4.4.7.1 Statistical Methods

The primary hypothesis of the Visceral Manifold Study is the number of subjects experiencing a major adverse event through 30 days will be less than a target performance goal (PG) of 50%. The PG was determined by using a conservative target that is approximately the average of the open surgical repair MAE rate calculated above (30.5%-77.4%, Table 6). The anticipated test device 30-day MAE rate was based on the current rate of MAE's (26%, Table 7) observed in 20 subjects meeting inclusion criteria into the primary study as of June 2016.

The sample size for the Visceral Manifold Study was determined using an exact method based on a one-sided 2.5% significance level and an anticipated 26% investigational device 30-day major adverse event rate. Based on these assumptions, a sample size from the pooled PS-IDE data of 46 subjects provides at least 80% power to test the primary hypothesis.

Table 6. Historical Comparison for Primary Safety Endpoint (MAE Rate at 30 days for Open Repair)

Reference	# of Patients	Mortality	Bowel Ischemia	Myocardial Infarction	Paraplegia	Renal Failure	Respiratory Failure	Stroke
Rigberg et al	1010	191 (19%)						
Becquemin et al	1678	90 (5.4%)	51 (3%)	20 (1.2%)	16 (1%)	289 (17.2%)	124 (7.4%)	12 (0.7%)
Murana et al	542	46 (8.5%)			22 (4.2%)			
Ferrer et al	257	16 (6.2%)			53 (20.8%)	31 (12.3%)	31 (12.3%)	
Bensley et al	450	45 (10%)		10 (2.4%)		48 (10.7%)	202 (45.1%)	9 (2.2%)
Nathan et al	83	6 (5.6%)						
Dayama et al	682	68 (10%)		87 (12.9%)		117 (17.2%)	286 (42%)	

Ferrante et al	200	5 (2.5%)		25 (12.8%)		22 (11%)	27 (13.8%)	
Tsilimparis et al	1091	58 (5.4%)		87 (8%)		109 (10%)	229 (21%)	
Piazza et al	7833	1331 (17%)			587 (7.5%)	1488 (19%)	2819 (36%)	
Total	13826	1855/13826	51/1678	229/4101	678/10310	2104/12191	3718/12191	21/2128
Rate of MAE at 30 Days for Open Surgical Repair		13.4%	3.0%	5.6%	6.6%	17.3%	30.5%	1.0%

Table 7. Historical Comparison for Expected Investigational Device 30 Day MAE Rate (Outcomes of subjects treated with the VTAAA stent graft system and meeting inclusion into the primary study as of June 2016)

Dataset	Mortality	Bowel Ischemia	Myocardial Infarction	Paraplegia	Renal Failure	Respiratory Failure	Stroke
Subjects meeting VMS PS-IDE I/E criteria	0/20 (0%)	0/20 (0%)	0/20 (0%)	2/20 (9.5%)	1/20 (5%)	3/20 (14%)	0/20 (0%)

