3.3.2 Open Surgical Repair

Open repair of thoracoabdominal aneurysms, especially in patients with preexisting comorbidities, is fraught with complications. A meta-analysis of 7,833 open repairs of thoracoabdominal aneurysm repairs from 2000 to 2010 found a 30 day mortality rate of 7%, in-hospital mortality of 10%, spinal cord ischemia rates of 7.5%, renal failure rates of 19%, and pulmonary dysfunction rates of 36%¹³. Predictors of adverse events after elective open repair based on pre-existing comorbidities have been established. Advanced age (>70 years)^{14,17}, respiratory disease¹⁶, renal insufficiency¹⁸, coronary artery disease^{14,17}, symptomatic aneurysms, extent 1 and 2 aneurysms¹⁹⁻²², and diabetes²³ are reported to be a predictor of 30-day mortality. Cardiac function²⁴, extent 1 and 2 aneurysms^{20,25-27}, symptomatic cases²⁷, and diabetes²³ are reported to be predictors of paraplegia. The outcomes reported above are in a low- to moderate- risk patient population. It is a logical extension to assume the outcomes in moderate- to high- risk patients would be worse.

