3.4 Benefits and Risks of Treatment Options

3.4.1 Open Surgical Repair

Contemporary series have shown that open repair of thoracoabdominal aneurysms, is associated with a significant mortality risk and increase in major complications. One report describes 7,833 open TAAA repairs from 2000 to 2010 found a 30 day mortality rate of 7%, in-hospital mortality of 10%, spinal cord ischemia rates of 7.5%, renal failure rates of 19%, and pulmonary dysfunction rates of 36%¹³. The risks of open repair are significantly higher than any other option for repair. Open repairs are durable but have substantial perioperative mortality and postoperative morbidity. Additionally, due to existing comorbidities and the high risk for complications this is not an option for many patients.

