4.4.3 Study Endpoints

The primary safety endpoint is freedom from major adverse events (MAE) at 30 days or during hospitalization if this exceeds 30 days.

Major adverse events include death, bowel ischemia, myocardial infarction, paraplegia, renal failure, respiratory failure, and stroke.

The primary effectiveness endpoint is the proportion of the study subjects with treatment success at 1 year. Treatment success is defined as a composite of technical success and freedom from the following:

- Aneurysm enlargement i.e., greater than 5mm as compared to any previous CT measure using orthogonal (i.e., perpendicular to the centerline) measurements
- Aneurysm rupture
- Aneurysm-related mortality
- Conversion to open repair
- Secondary intervention for migration, Type I and III endoleaks, device integrity failure (e.g., fracture), and patency-related events (i.e., device component stenosis or occlusion and embolic events)

Secondary endpoints include:

- Technical success and the individual components of technical success:
 - Successful delivery
 - Deployment at the intended implantation site
 - Patency of all endovascular graft and stent components
 - Absence of device deformations requiring unplanned placement of an additional device
 - Absence of inadvertent covering of aortic branch vessels
 - Successful withdrawal

- Freedom from the individual components of the primary safety endpoint at 30 days:
 - Death
 - Bowel ischemia
 - Myocardial infarction
 - Paraplegia
 - Renal failure
 - Respiratory failure
 - Stroke
- Freedom from paraparesis at 30 days
- The following at each follow-up interval:
 - Treatment success and the individual components of treatment success including freedom from the following:
 - Aneurysm enlargement
 - Aneurysm-related mortality
 - Aneurysm rupture
 - Conversion to open repair
 - Secondary intervention for migration, type I and III endoleaks, device integrity failure (i.e., fracture), and patency-related events (i.e., device stenosis or occlusion and embolic events).
 - Renal failure
 - All-cause mortality
 - Endoleaks
 - Device integrity failure (e.g., fracture)

- Patency-related events (i.e., device stenosis or occlusion and embolic events)
- Other device-related events

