4.4.7 Data Presentation and Analysis Plan

The primary purpose of this study is to evaluate the safety of this device as there are no or very limited devices and clinical options available for this patient population. The primary safety endpoint of this study is safety freedom from major adverse events (MAE) at 30 days or during hospitalization if this exceeds 30 days. Major adverse events include death, bowel ischemia, myocardial infarction, paraplegia, renal failure, respiratory failure, and stroke. The primary safety endpoint will be analyzed to determine statistical significance when compared to a target performance goal. A literature review of outcomes of open surgical repair was used to create the performance goal as there is not a comparable endovascular option to use for analysis. The performance goal was selected based on the range of subjects experiencing a major adverse event at 30 days. The range was calculated based on assumptions of the minimum and maximum number of subjects experiencing at least one MAE in the historical open surgical repair group (Table 6). Based on the literature reviewed and the above assumptions the range of subjects experiencing at least one MAE in the open surgical repair group is 30.5% to 77.4%.

The primary effectiveness endpoint is the proportion of the study subjects with treatment success at 1 year. The data will be presented as quality outcomes with the number of study subjects with treatment success compared to the overall patient population.

Additionally, data outcomes from this study will be entered into a common vascular database so that data can be pooled with other PS-IDEs. This would provide consistent reporting across the PS-IDEs. Additionally, the PS-IDEs will be evaluating the same device and endpoints to allow for a poolability of data across the sites.

The pooled data will be separated into two separate study arms: primary study arm and expanded selection arm.

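### Table 6 enters 17% mortality for its 7,833-patient open-repair source where the protocol's own text gives 7% at 30 days, so the 77.4% upper end behind the 50% goal is misstated

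*Combined protocol and SAP*

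**What the plan says.** Section 4.4.7 explains the choice of goal: "The performance goal was selected based on the range of subjects experiencing a major adverse event at 30 days". It then reports that "the range of subjects experiencing at least one MAE in the open surgical repair group is 30.5% to 77.4" percent, a range built on assumptions about the minimum and maximum number of patients with at least one event. Section 4.4.7.1 calls the goal conservative and describes it as "approximately the average of the open surgical repair MAE rate calculated above (30.5%-77.4%, Table 6"). The primary hypothesis is that the number of subjects "experiencing a major adverse event through 30 days will be less than a target performance goal (PG) of 50" percent.

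Table 6 is titled "Historical Comparison for Primary Safety Endpoint (MAE Rate at 30 days for Open Repair"). For its 7,833-patient source it prints 1331 deaths (17%), 7.5% paraplegia, 19% renal failure and 36% respiratory failure. The pooled mortality is printed as 1855/13826, or 13.4%.

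The background sections describe that source differently on mortality alone. Section 3.3.2, on 7,833 open repairs, gives "30 day mortality rate of 7%, in-hospital mortality of 10%, spinal cord ischemia rates of 7.5%, renal failure rates of 19" percent, and pulmonary dysfunction of 36%. Section 3.4.1 repeats it: "One report describes 7,833 open TAAA repairs from 2000 to 2010 found a 30 day mortality rate of 7%, in-hospital mortality of 10" percent.

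The endpoint in section 4.4.3 has a somewhat longer window than the table: "freedom from major adverse events (MAE) at 30 days or during hospitalization if this exceeds 30 days".

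**The concern.** The two descriptions are of the same source. The number of repairs is the same, the three companion rates agree, and the reference cited in sections 3.3.2 and 3.4.1 corresponds to the Table 6 row. Only mortality disagrees, and 17% appears in neither background section.

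The cell carries weight because this source supplies 7,833 of the 13,826 patients and 1331 of the 1856 listed deaths (72%). It feeds the pooled mortality, then the upper end of the range, then the average that is the only stated basis for the null value of the primary safety test. The data are also to be pooled with other investigations of the device and used to develop a pivotal study (section 4.4.6), so a wrong historical rate could be carried forward.

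**Working it through.** **Inputs.** All counts are from Table 6. The 7% and 10% are from sections 3.3.2 and 3.4.1. The 50% goal, 26% anticipated rate, one-sided 2.5% level and N = 46 are from section 4.4.7.1.

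**1. Reproduce the printed range.** The plan does not print its formula. Taking the upper end as the sum of the seven pooled rates (no patient has two events) and the lower end as the largest single rate reproduces both figures:

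- Upper end: 13.4 + 3.0 + 5.6 + 6.6 + 17.3 + 30.5 + 1.0 = 77.4%.
- Lower end: respiratory failure, 3718/12191 = 30.5%.
- Unrounded, the six rates other than mortality are 3.04 + 5.58 + 6.58 + 17.26 + 30.50 + 0.99, which total 63.94% before rounding of the parts. Adding 1855/13826 = 13.42% gives 77.36%.
- Implied midpoint: (30.50 + 77.36)/2 = 53.93%. The protocol prints no midpoint; this is my calculation.

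**2. Check the mortality column.**

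- The nine other rows: 191 + 90 + 46 + 16 + 45 + 6 + 68 + 5 + 58 = 525.
- With the large source: 525 + 1331 = 1856. The printed total is 1855.
- The 83-patient row prints 6 (5.6%), but 6/83 = 7.2%. Five deaths there would bring the column to exactly 1855, although 5/83 = 6.0% does not match 5.6% either. The documents do not settle which entry is wrong.

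**3. Replace 17% by the stated 30-day rate.** 0.07 × 7833 = 548 deaths.

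- Pooled mortality: (525 + 548)/13826 = 1073/13826 = 7.76%. If the column is one death lower, 1072/13826 = 7.75%.
- Upper end: 63.94 + 7.76 = 71.70%. (Adding the rounded rates gives 71.8%.)
- Midpoint: (30.50 + 71.70)/2 = 51.10%.

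**4. The endpoint's longer window.** For death within 30 days or in hospital, the stated figures only bound the rate. If both apply to the same 7,833 patients, it is at least 10% (783 deaths) and reaches 17% only if the two groups of deaths do not overlap at all.

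- Pooled mortality, minimum: 1308/13826 = 9.46% (or 1307/13826 = 9.45%).
- Upper end: at least about 63.94 + 9.46 = 73.4%.
- Midpoint: at least about 51.9% (51.95% both ways before the second decimal is dropped, so a minimum should not be rounded up to 52.0%).

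| Mortality used for the 7,833 | Pooled mortality | Range | Midpoint | Midpoint minus 50% |
|---|---|---|---|---|
| 17%, as printed | 13.4% | 30.5%–77.4% | 53.9% | 3.9 |
| 7%, 30 days | 7.8% | 30.5%–71.7% | 51.1% | 1.1 |
| 10%, minimum for the longer window | at least 9.5% | 30.5% to at least 73.4% | at least 51.9% | at least 1.9 |

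**5. Effect on the test.** With N = 46, a null rate of 50% and a true rate of 26%, the exact one-sided test rejects at 15 or fewer events, with actual level 0.0129 and power 88.1%. None of this uses Table 6 except through the 50%, which is pre-set and does not move.

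**The case against.** The best defence is that the error changes no decision. The plan claims only that 50% is approximately the average of the range and is conservative, and both stay true at every midpoint from 51.1% to 53.9%. The upper end is an assumed ceiling rather than an estimate, so moving it by 4 to 6 points in a range about 47 points wide matters little. The 15-patient study is described as preliminary, and the test is sized on pooled data. All of this stands, and it is why the severity is low. It does not make the printed figure right: the table is labelled 30-day, the documents' 30-day rate for this source is 7%, and the range is quoted as the basis of the goal.

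It can also be said that the endpoint extends through hospitalization, so a figure above 7% may be legitimate. That stands for the endpoint, but not for a table and hypothesis worded as 30-day. Even on the longer window, 17% needs zero overlap between the two groups of deaths. The 10% floor has its own limit, because section 3.3.2 calls the source a meta-analysis and gives no separate denominators.

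Two stronger readings are tempting. One is that the authors added 7% and 10%. The sum fits, but 1331 is also simply 17% of 7,833 with the decimal dropped (1331.6), and only the source can show where 17% came from. The other is that the 50% goal is too lenient or the sample size wrong. The documents do not support that: 50% remains below the recomputed midpoint in every case, and the level, power and N do not depend on the cell.

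**Conclusion.** The contradiction is real and no other section resolves it. On the table's own 30-day window, pooled open-repair mortality should read 7.8% rather than 13.4%, and the upper end 71.7% rather than 77.4%, a fall of about 5.7 points (77.36 − 71.70 = 5.66). The margin behind the word conservative drops from about 4 points to about 1. The consequence stops at the stated historical rate, the range and that margin. The conclusion assumes that the 7% in sections 3.3.2 and 3.4.1 is faithful to the source, and that the upper end is the sum of the pooled rates, which the reproduction in step 1 supports. The longer-window figures further assume one common denominator for both mortality rates. Low severity: correction of a stated figure.

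**What to change.** 1. Check the 7,833-patient source, then enter one mortality measure that matches the 30-day window in the table title. If 7% is confirmed, enter 548 (7%), a total of 1072 or 1073 of 13826 according to item 3, and 7.8%. Restate the range in sections 4.4.7 and 4.4.7.1 as 30.5% to 71.7%.
2. If the table is instead meant to cover 30 days or hospitalization if longer, relabel it and take the combined figure from the source. If only 10% is available, mark it as a minimum, state the assumption that both rates apply to the same 7,833 patients, and give the upper end as at least about 73.4%.
3. Reconcile the printed total of 1855 with the column sum of 1856, starting with the 83-patient row. The one-death gap changes no pooled rate at one decimal.
4. Keep the 50% goal, the test and N = 46. No sentence on the distance between the goal and the midpoint is needed, since that distance depends on which window is chosen.

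The cost is one source check, one or two cells, one total with its rate, and the range in two sentences. The design, goal, test and sample size are untouched.

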4.4.8 Limitations of the Study

Limitations of the study are that it is a single center study with a small patient population. We aim to curb this limitation by pooling our data with other IDE holders.

4.5 Risk Analysis

The risk analysis includes a description and analysis of all increased risks to the research subjects and how these risks will be minimized. The risks can be separated into three categories: procedural-related risks, device performance-related risks, and device material-related risks.

4.5.1 Potential Risks

4.5.1.1 Procedural-related risks

Procedural related risks including general and device specific procedural risks can result in several serious harms to the patient including contrast damage, allergic response, paraplegia, peripheral

nerve damage, injury to access vessel, dislodging of thrombus, dissection or further dissection of vessel, rupture of a dissection, embolism, branch artery or parenchyma damage of ischemia, inadvertent internal iliac occlusion or ischemic colitis, radiation injury from the laser if used including redness or burns to the skin, system effects including increased risk of morbidity and mortality, local effects at the access site including wound infection, hematomas, seromas, arterial or venous damage, failure to access the aorta, inaccurate deployment of devices, failure to deploy devices, and displacement of devices. These risks can be mitigated in a number of ways including strict adherence to the investigational protocol, patient eligibility criteria, procedures performed by trained and qualified physicians, use of standard surgical and endovascular techniques, and regular follow-ups. Although the risk is lowered by following these mitigation strategies the risk cannot be completely eliminated. However, the potential benefit of the manifold system as compared to other surgical techniques outweighs the potential procedural related risks to the patient.

4.5.1.2 Material-related risks

Material related risks are risks that are associated with physical components of the stent graft including risks related to stent breakage, branch vessel stent crush, barb fracture, fabric wear, biocompatibility, and sterility. Risks of these components include vessel occlusion, embolism, component separation, migration, and infection. These risks can be mitigated several ways including careful case planning for patient selection, device placement, proper sizing, use of compatible components, and regular follow-ups to identify early evidence of migration or separation.

4.5.1.3 Performance related risks

There are performance risks of the modular components succumbing to material fatigue resulting in component separation, endoleak or endotension, graft occlusion, kinking, or migration. These risks can be mitigated several ways including adhering to industry standard seal zone lengths,

proper oversizing, lining branch stents with self-expanding stents, regular follow-ups to identify early evidence of migration or separation and allow for appropriate treatment, by the use of completion angiography coupled with cuffs, ballooning, or additional stent grafts if evidence of endoleak.

4.5.1.4 Actual Risk Realized While the stent graft design is intuitive, there is a learning curve with respect to the procedural considerations, necessary site infrastructure and post-operative management of patients treated with an endovascular TAAA therapy. During initial enrollment, actual risks observed include but were not limited to renal injury/failure, respiratory failure, paraplegia, and all-cause mortality. Although these risks are considered anticipated, the events are serious in nature and thus warrant investigation and consideration of appropriate corrective and preventative actions. The exact cause of each event and sequela of events within a given subject are difficult to extrapolate; however, lessons were learned during the first four cases in this series.

The target patient population of this study can represent challenges such as advanced age, presence of significant co-morbidities, and in some cases complex aortic anatomy. Anatomical challenges may influence operative variables (i.e. procedure time, blood loss, fluoroscopy time, and contrast volume) which may further exacerbate baseline co-morbidities and impact post-operative outcomes. The first four subjects treated under the study each presented baseline and operative challenges that may have affected outcome. From these experiences, lessons were learned, and mitigation strategies aimed to reduce risks identified.

With respect to the actual risks observed, several mitigation strategies will be implemented from patient selection, procedural considerations and site infrastructure perspectives. Procedural complexity is amplified substantially by arch anatomy either from right upper extremity access or from a type III arch with left upper extremity access, limiting subject selection. Parallax alterations are frequent and

compulsatory in toggling between branch access and Endo bypass deployment to prevent excessive coverage of branch vessels. Embolic risks from dislodging soft thrombus prevents selection of patients with suspected acute thrombus formation within the Visceral aorta. Patients are routinely affected by pulmonary complication making emphasis on pulmonary reserve a valued aspect of patient's selection.

Procedural considerations and site infrastructure changes will also be implemented to mitigate the risk of paraplegia and renal injury/failure. To address paraplegia, a standardized staging protocol will be used in subjects deemed high risk for spinal cord ischemia. Also, at physician's discretion, for anatomies with retrograde collateral circulation into the internal iliac arteries, the femoral sheath may be removed after deployment of the manifold to lighten the severity of ischemia. Renal function can be negatively impacted by operative variables and volume loading during the procedure. Furthermore, vessel anatomy and visualization can create a challenge during the procedure that can impact overall procedure time, contrast volume administered and increase risk of vessel injury. A commercially available 3-dimensional overlay with CT image interface may help prevent such a problem in the future. This should allow definition of the ostium with any angle of the image intensifier and would allow easier branch cannulation but also assessment of depth of penetration with AP imaging prior to stent deployment. Additionally, CO₂ may be used as an alternative to iodinated contrast material.

Additional mitigation strategies implemented to improve patient safety include external reviewer assessment of pre-operative CT scans, use of a central DSMB consistent with other parallel PS-IDEs, and frequent sharing of lessons learned between PS-IDE Investigators regarding safety and effectiveness.

